12.2. Participant Information and Consent

All parties will ensure protection of participant personal data and will not include participant names or other identifiable data in any reports, publications, or other disclosures, except where required by law.

When study data are compiled for transfer to Pfizer and other authorized parties, participant names, addresses, and other identifiable data will be replaced by numerical codes based on a numbering system provided by Pfizer in order to de-identify study participants. The investigator site will maintain a confidential list of participants who participated in the study, linking each participant's numerical code to his or her actual identity. In case of data transfer, Pfizer will maintain high standards of confidentiality and protection of participants' personal data consistent with applicable privacy laws.

The informed consent document and any participant recruitment materials must be in compliance with ICH GCP, local regulatory requirements, and legal requirements, including applicable privacy laws.

The ICD will contain a separate section that addresses the use of remaining mandatory samples for optional additional research. The optional additional research does not require the collection of any further samples. The investigator or authorized designee will explain to each participant the objectives of the additional research. Participants will be told that they are free to refuse to participate and may withdraw their consent at any time and for any reason during the storage period. A separate signature will be required to document a participant's agreement to allow any remaining specimens to be used for additional research. Participants who decline to participate in this optional research will not provide this separate signature.

The informed consent document used during the informed consent process and any participant recruitment materials must be reviewed and approved by Pfizer, approved by the IRB/EC before use, and available for inspection.

The investigator must ensure that each study participant is fully informed about the nature and objectives of the study and possible risks associated with participation.

The investigator, or a person designated by the investigator, will obtain written informed consent from each participant before any study-specific activity is performed. The investigator will retain the original of each participant's signed consent document.

12.3. Reporting of Safety Issues and Serious Breaches of the Protocol or ICH GCP

In the event of any prohibition or restriction imposed (ie, clinical hold) by an applicable regulatory authority in any area of the world, or if the investigator is aware of any new

information that might influence the evaluation of the benefits and risks of the study intervention, Pfizer should be informed immediately.

In addition, the investigator will inform Pfizer immediately of any urgent safety measures taken by the investigator to protect the study participants against any immediate hazard, and of any serious breaches of this protocol or of ICH GCP that the investigator becomes aware of.

13. DEFINITION OF END OF TRIAL

13.1. End of Trial in a Member State

End of trial in a Member State of the European Union is defined as the time at which it is deemed that a sufficient number of participants have been recruited and completed the study (last participant last visit [LPLV]) as stated in the regulatory application (ie, clinical trial application [CTA]) and ethics application in the Member State. Poor recruitment (recruiting less than the anticipated number in the CTA) by a Member State is not a reason for premature termination but is considered a normal conclusion to the study in that Member State.

13.2. End of Trial in All Other Participating Countries

End of trial in all other participating countries is defined as LPLV.

14. SPONSOR DISCONTINUATION CRITERIA

Premature termination of this study may occur because of a regulatory authority decision, change in opinion of the IRB/EC, safety problems, or at the discretion of Pfizer. In addition, Pfizer retains the right to discontinue development of fidanacogene elaparvovec and giroctocogene fitelparvovec at any time.

If a study is prematurely terminated, Pfizer will promptly notify the investigator. After notification, the investigator must contact all participating participants and the hospital pharmacy (if applicable). As directed by Pfizer, all study materials must be collected and all CRFs completed to the greatest extent possible.

15. PUBLICATION OF STUDY RESULTS

15.1. Dissemination of Clinical Study Data

Pfizer fulfills its commitment to publicly disclose clinical study results through posting the results of studies on www.clinicaltrials.gov (ClinicalTrials.gov), the EudraCT/CTIS, and/or www.pfizer.com, and other public registries and websites in accordance with applicable local laws/regulations. In addition, Pfizer reports study results outside of the requirements of local laws/regulations pursuant to its SOPs.

In all cases, study results are reported by Pfizer in an objective, accurate, balanced, and complete manner and are reported regardless of the outcome of the study or the country in which the study was conducted.

www.clinicaltrials.gov

Pfizer posts clinical trial results on www.clinicaltrials.gov for Pfizer-sponsored interventional studies (conducted in patients) that evaluate the safety and/or efficacy of a product, regardless of the geographical location in which the study is conducted. These results are submitted for posting in accordance with the format and timelines set forth by US law.

EudraCT/CTIS

Pfizer posts clinical trial results on EudraCT/CTIS for Pfizer sponsored interventional studies in accordance with the format and timelines set forth by EU requirements.

www.pfizer.com

Pfizer posts CSR synopses and plain-language study results summaries on www.pfizer.com for Pfizer-sponsored interventional studies at the same time the corresponding study results are posted to www.clinicaltrials.gov. CSR synopses will have personally identifiable information anonymized.

Documents within marketing applications

Pfizer complies with applicable local laws/regulations to publish clinical documents included in marketing applications. Clinical documents include summary documents and CSRs including the protocol and protocol amendments, sample CRFs, and SAPs. Clinical documents will have personally identifiable information anonymized.

Data sharing

Pfizer provides researchers secure access to participant-level data or full CSRs for the purposes of “bona-fide scientific research” that contributes to the scientific understanding of the disease, target, or compound class. Pfizer will make data from these trials available 18 months after study completion. Participant-level data will be anonymized in accordance with applicable privacy laws and regulations. CSRs will have personally identifiable information anonymized.

Data requests are considered from qualified researchers with the appropriate competencies to perform the proposed analyses. Research teams must include a biostatistician. Data will not be provided to applicants with significant conflicts of interest, including individuals requesting access for commercial/competitive or legal purposes.

15.2. Publications by Investigators

For multicenter trials, the primary publication will be a joint publication developed by the investigator and Pfizer reporting the primary endpoint(s) of the study covering all study sites. The investigator agrees to refer to the primary publication in any subsequent publications. Pfizer will not provide any financial compensation for the investigator’s participation in the preparation of the primary congress abstract, poster, presentation, or primary manuscript for the study.

Investigators are free to publish individual center results that they deem to be clinically meaningful after publication of the overall results of the study or 12 months after primary completion date or study completion at all sites, whichever occurs first, subject to the other requirements described in this section.

The investigator will provide Pfizer an opportunity to review any proposed publication or any other type of disclosure of the study results (collectively, “publication”) before it is submitted or otherwise disclosed and will submit all publications to Pfizer 30 days before submission. If any patent action is required to protect intellectual property rights, the investigator agrees to delay the disclosure for a period not to exceed an additional 60 days upon request from Pfizer. This allows Pfizer to protect proprietary information and to provide comments, and the investigator will, on request, remove any previously undisclosed confidential information before disclosure, except for any study intervention or Pfizer related information necessary for the appropriate scientific presentation or understanding of the study results. For joint publications, should there be disagreement regarding interpretation and/or presentation of specific analysis results, resolution of, and responsibility for, such disagreements will be the collective responsibility of all authors of the publication.

For all publications relating to the study, the investigator and Pfizer will comply with recognized ethical standards concerning publications and authorship, including those established by the International Committee of Medical Journal Editors. The investigator will disclose any relationship with Pfizer and any relevant potential conflicts of interest, including any financial or personal relationship with Pfizer, in any publications. All authors will have access to the relevant statistical tables, figures, and reports (in their original format) required to develop the publication.

Appendix 1. Abbreviations

This following is a list of abbreviations that may be used in the protocol.

Abbreviation	Term
AAV	adeno-associated virus
AAV2/6	adeno-associated virus 2/6
AAV6	adeno-associated virus vector 6
AAV-Spark100	Bioengineered AAV capsid, derived from a naturally occurring AAV serotype
AAV-Spark100-hFIX19-Padua	Adeno-associated viral vector comprised of the Spark100 AAV capsid encoding hFIX-Padua
ABR	Annualized Bleeding Rate
AIR	Annualized Infusion Rate
AE	adverse event
AST	Aspartate Transaminase
BDD	B-domain deleted
BU	Bethesda Unit
CAF	Contact Authorization Form
CD4+	Cluster of Differentiation 4 positive
cDNA	Complementary DNA
CFR	Code of Federal Regulations
CONSORT	Consolidated Standards of Reporting Trials
COVID-19	Coronavirus disease 2019
CRF	case report form
CSA	clinical study agreement
CSR	clinical study report
CT	clinical trial
CTA	clinical trial application
EC	ethics committee
EDP	exposure during pregnancy
eCRF	Electronic case report form
ESI	Events of Special Interest
EU	European Union
EudraCT	European Clinical Trials Database
FIX	Factor IX
FIX:C	Factor IX Circulating
FVIIa	Factor VIIa
FVIII	Factor VIII
FVIII:C	Factor VIII Circulating
GCP	Good Clinical Practice
HBc	Hepatitis B Core
HBsAg	Hepatitis B Surface Antigen
HBV-DNA	Hepatitis B Virus – Deoxyribonucleic Acid
HCV	Hepatitis C Virus

Abbreviation	Term
HCV-RNA	Hepatitis C Virus –Ribonucleic Acid
hFVIII	human FVIII
HIV	human immunodeficiency virus
IA	interim analysis
ICD	Informed Consent Document
ICH	International Council of Harmonization
ID	identification
IgG	Immunoglobulin G
IND	investigational new drug application
IRB	institutional review board
IU	international unit
LOE	Lack of Efficacy
LPLV	last participant last visit
MAH	marketing authorization holder
MoH	Ministry of Health
N	number
N/A	not applicable
nAb	neutralizing antibody
PACL	protocol administrative change letter
PCD	primary completion date
PI	principal investigator
QTL	quality tolerance limit
rAAV2/6	Recombinant adeno-associated virus 2/6
RBC	Red blood cell
SAE	serious adverse event
SAP	statistical analysis plan
SB-525 (rAAV6-hFVIII-BDD)	Adeno-associated viral vector comprised of AAV6 capsid encoding hFVIII-BDD
SOC	standard of care
SOP	standard operating procedure
SRSD	single reference safety document
SUSAR	suspected unexpected serious adverse reactions
US	United States

Appendix 2. Bleed and Factor Replacement Regimen Definitions^{1,2,3}

Definition of a Bleed (for analysis purposes)

Treated Bleed: An event necessitating administration of coagulation factor within 72 hours of signs or symptoms of bleeding (protocol definition, unless specifically referring to untreated bleed).

Untreated Bleed: A bleeding event not necessitating administration of coagulation factor within 72 hours of signs or symptoms of bleeding.

New Treated Bleed: A treated bleed occurring >72 hours after stopping treatment from the original bleed for which treatment was initiated or a treated bleed occurring at a different site from the original bleed regardless of the time from last injection.

New Untreated Bleed: An untreated bleed occurring >72 hours after the previous untreated bleed at the same site or occurring >72 hours after stopping treatment from the original bleed for which treatment was initiated, or an untreated bleed occurring at a different site from the original bleed regardless of the time from last bleed or last injection.

Definition of a Bleed Location

Target Joint: Defined as a major joint (eg, hip, elbow, wrist, shoulder, knee, and ankle) into which repeated bleeds occur (three or more spontaneous bleeds into a single joint within a consecutive 6-month period). A target joint is considered resolved when there are ≤ 2 bleeds into the joint within a 12-month period.

Joint Bleed: A bleeding episode characterized by rapid loss of range of motion as compared with baseline that is associated with any combination of the following: pain or an unusual sensation in the joint, palpable swelling, and warmth of the skin over the joint.

Muscle Bleed: An episode of bleeding into a muscle, determined clinically and/or by imaging studies, generally associated with pain and/or swelling and functional impairment.

Definition of Bleed Types

Spontaneous Bleeds: Bleeding for no apparent/known reason particularly into the joints, muscles, and soft tissues.

Traumatic Bleeds: Bleeding event occurring for an apparent/known reason.

Note: Bleeds related to a procedure/surgery such as hematomas/bruising resulting from any surgeries or invasive procedures (eg, tooth extractions, venipuncture, or subcutaneous drug administrations) or invasive diagnostic procedures (eg, lumbar puncture, endoscopy with biopsy) would NOT be counted as bleeds. Bleeds related to procedure/surgery are not associated with any trauma except procedure/surgery-induced trauma.

Definition of Factor Replacement Regimens

Prophylaxis Therapy: The regularly scheduled and regimented administration of factor replacement therapy to prevent bleeding.

Preventative Therapy: Infusion of clotting factor that is given in anticipation of a planned physical activity that has a high risk of injury (eg, surgery or sporting activity).

On-Demand Therapy: The administration of factor replacement therapy only at the time of an acute bleeding event.

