3. ENDPOINTS AND BASELINE VARIABLES: DEFINITIONS AND CONVENTIONS

3.1. Primary Endpoint(s)

The primary endpoint is ABR (treated and total). A bleeding episode is defined in Protocol Appendix 2.

If a bleed is treated with FIX infusion (for Hemophilia B) or FVIII infusion (for Hemophilia A) (according to Bleeding eDiary or Bleeding CRF) within 72 hours post the start of bleeding (by comparing date/time of bleeding to date/time of infusion in Infusion eDiary or Infusion CRF), regardless of the type of treatment (preventive, prophylaxis or rescue medication), it will be considered as a treated bleed. If a bleed is not treated with FIX/FVIII infusion according to the Bleeding eDiary or the Bleeding CRF, the bleed will not be considered as a treated bleed but considered as an untreated bleed.

If there are multiple concurrent bleeds (spontaneous or traumatic) on the same date AND time but in different locations in a participant, they will be recorded as one bleed for that participant. If concurrent bleeds occurred on the same day but at different times and different locations, they will be counted as separate bleeds. Only new bleeds (as defined in Protocol Appendix 2) will be counted toward the number of bleeds for ABR calculation.

For untreated bleed, every occurrence will be counted as a separate bleed.

The ABR per participant based on prospectively collected bleeds will be calculated as:

The number of bleeds (all treated bleeding episodes including spontaneous and traumatic) x 365.25 days/number of days during the observation time period while the participant received prophylaxis factor replacement therapy in the usual care setting from baseline visit (Day 1) to end of study (date of study completion or discontinuation, whichever is earlier).

Number of bleeds (treated bleeds and all bleeds, respectively) and infusions within the last 12 months will be collected at the screening visit using hemophilia history CRF for all participants enrolled under Protocol Amendment 5 (01 Oct 2020) or under a subsequent protocol amendment. Thus the retrospectively collected ABR per participant will be equal to number of bleeds in the past 12 months collected in the Hemophilia History form.

Participants enrolled in hemophilia A cohort or hemophilia B cohort prior to Protocol Amendment 5 will not have the CRF retrospectively filled out.

ABR combining retrospective and prospective data will be calculated as:

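### No rule links an entry recorded as untreated to a later treated entry at the same site, so one episode logged as two entries counts twice in total ABR

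*Protocol*

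**What the plan says.** Protocol Appendix 2 defines a treated bleed as "An event necessitating administration of coagulation factor within 72 hours of signs or symptoms of bleeding". A treated bleed is new on one of two limbs. The first is time since an earlier treatment: "New Treated Bleed: A treated bleed occurring >72 hours after stopping treatment from the original bleed for which treatment was initiated". The second is location: "or a treated bleed occurring at a different site from the original bleed regardless of the time from last injection". The definition of a new untreated bleed is wider and looks back at both kinds of predecessor: "An untreated bleed occurring >72 hours after the previous untreated bleed at the same site or occurring >72 hours after stopping treatment" of the original bleed, or a different site.

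SAP 3.1 makes ABR, treated and total, the primary endpoint, and SAP 6.1.1 analyses both. On counting, SAP 3.1 has four relevant rules:

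- A bleed is treated if the bleeding diary or CRF shows factor treatment and an infusion is found "within 72 hours post the start of bleeding".
- "If a bleed is not treated with FIX/FVIII infusion according to the Bleeding eDiary or the Bleeding CRF, the bleed will not be considered" treated, and it is classed as untreated.
- "Only new bleeds (as defined in Protocol Appendix 2) will be counted toward the number of bleeds for ABR calculation".
- Entries classed as untreated have a rule of their own: "For untreated bleed, every occurrence will be counted as a separate bleed".

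Its rules for concurrent bleeds deal with different locations only.

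**The concern.** There are four possible same-site sequences of two entries. Appendix 2 sets a 72-hour limit for treated then treated, treated then untreated, and untreated then untreated. It has none for untreated then treated. That gap matters when a participant logs a bleed as untreated, the bleed does not settle, and he logs it again the next day as treated. Appendix 2's own definition of a treated bleed, with its 72-hour clock running from the first signs, makes this one bleed. The counting rules do not bring the two entries together.

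At stake is total ABR and, through SAP 3.2, the overall annualized bleed rate. Protocol Section 1.2 says the prophylaxis data from this study will be the control for the gene therapy studies, so an inflated count would raise the control rate.

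**Working it through.** The plan states no figure that depends on this rule, and SAP 5.1 plans no hypothesis test, so there is no sample size or error rate to reproduce. The check applies the counting rules to short same-site sequences.

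**Inputs.** The 72-hour window and the definitions of new bleeds come from Appendix 2. The status rule, the new-bleeds-only rule and the rule on untreated occurrences come from SAP 3.1. The ordinary reading of a new treated bleed is used: a treated bleed with no earlier treated bleed is itself the original.

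**Counts.** Times are hours from the first signs.

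| Same-site record | How status is set | Treated | Total |
|---|---|---|---|
| One entry, factor at 24 h | either way | 1 | 1 |
| Untreated entry at 0 h, treated entry at 24 h, factor at 25 h | diary/CRF status decides | 1 | 2 |
| Same two entries | infusion time alone | 1 | 1 |
| Same two entries | with a linking rule | 1 | 1 |

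In the second row the steps are:

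1. The first entry is untreated according to the diary or CRF, so SAP 3.1 classes it as untreated.
2. Every untreated occurrence counts, so it adds 1 to the total.
3. The second entry has an infusion 1 hour after its own start, so it is treated. No treated bleed precedes it, so it counts and adds 1 to treated and 1 to total.
4. Factor was given 25 hours after the first signs. By Appendix 2 the episode is one treated bleed, so the total should be 1.

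Two neighbouring cases fall outside this point. A single entry with factor at 96 h counts as treated 0, total 1, because of the 72-hour window and not because of a missing link. Entries at 0 h (untreated) and 80 h (treated, factor at 81 h) count as treated 1, total 2, but factor came more than 72 hours after the first signs, so Appendix 2 does not make them one treated bleed.

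**Weight of one extra bleed in a participant's ABR**, 365.25/days:

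- 180 days: 365.25/180 = 2.03 per year
- 120 days: 365.25/120 = 3.04 per year (SAP 2.2 allows follow-up below 6 months)
- 365.25 days: 1.00 per year

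**Cohort effect (assumption only).** Let T be the true treated rate, U the true untreated rate and f the share of treated bleeds first logged as untreated. The relative rise in total ABR is f × T/(T + U). With T = U = 4 per year:

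- f = 10%: (4 + 4 + 0.4)/8 = 1.05, a rise of 5%
- f = 25%: (4 + 4 + 1)/8 = 1.125, a rise of 12.5%
- f = 50%: (4 + 4 + 2)/8 = 1.25, a rise of 25%

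The values of T, U and f are not in the documents.

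**The case against.** The strongest objection is that SAP 3.1 compares bleed times with infusion times, whatever the purpose of the infusion. In the example the infusion lies within 72 hours of the first entry as well. Matched on time alone, both entries would be treated bleeds at one site and would merge to one. That is correct as arithmetic, but the SAP does not match on time alone. It conditions on the diary or CRF, and its next sentence makes an entry untreated when those records say so.

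It can also be said that the fault needs two entries for one episode, and that sites have chances to notice. Protocol 5.2 and 6.3 call for diary compliance review at least monthly, Section 8.2.1 has the investigator review diary bleeds, and Section 6.5 adds a review at the end of study. The first part stands and limits the point. The reviews may reduce the number of duplicates, but nothing tells the site or the programmer how to count a pair that remains.

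A reader might infer three stronger things that the documents do not support:

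- **That such bleeds drop out of treated ABR.** This requires a treated bleed to meet one of the two limbs whenever any same-site bleed came before. The first limb compares with an original treated bleed. Where none exists, the bleed is itself the original. Taken that literally, the text would also discard a participant's first treated bleed, and the SAP numerator is all treated episodes.
- **That the count depends on the order of logging.** Appendix 2 alone would merge a treated entry followed within 72 hours by an untreated one. SAP 3.1's sentence on untreated occurrences counts both there too, so the asymmetry disappears.
- **That the gene therapy comparison is biased by a known amount.** That depends on counting rules in C0371002 and C3731003, which are not in these documents.

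**Conclusion.** The point holds in a limited form. Followed as written, the rules give a total of 2 for one episode when it is logged as untreated and then as treated at the same site, with factor given within 72 hours of the first signs. Total ABR is overstated by one bleed for each such episode, or 2.03 per year for a participant followed for 180 days. Treated ABR is unaffected on the ordinary reading.

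The rule on untreated occurrences keeps the first entry in the total, and it also conflicts with Appendix 2's 72-hour limit for repeat untreated bleeds. Correcting that sentence alone would not close the gap: the first entry would still qualify as an untreated bleed, and nothing would tie the second entry to it.

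The effect on the cohort is unknown. The 5% to 25% range rests wholly on the assumed shares and on equal numbers of treated and untreated bleeds.

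**What to change.** Add a rule to SAP 3.1 and Protocol Appendix 2, for example:

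> If an entry recorded as untreated is followed by a treated entry at the same site, and the factor infusion for the treated entry falls within 72 hours of the start of the first entry, the two entries are one treated bleed starting at the first entry. It is counted once in treated ABR and once in total ABR, and the first entry is not counted as an untreated bleed.

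The condition should be on the infusion time, not on the start of the second entry. Otherwise a second entry at 70 hours with factor at 130 hours would become a bleed treated 130 hours after onset, against the 72-hour definition.

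State that the rule is an exception to "For untreated bleed, every occurrence will be counted as a separate bleed", and reconcile that sentence with Appendix 2's definition of a new untreated bleed.

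The cost is a short text change and a small programming change, using the bleed location and the bleed and infusion times already collected. The downside is that two truly separate bleeds at one site within 72 hours would be merged, which Appendix 2 already accepts for the other sequences.

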3.2. Secondary Endpoint(s)

The AIR per participant will be calculated as:

The number of infusions received x 365.25 days/number of days during the observation time period while participant received prophylaxis factor replacement therapy in the usual care setting from baseline visit (Day 1) to end of study (date of study completion or discontinuation, whichever is earlier).

Similarly as ABR (Section 3.1), the retrospectively collected AIR per participant will be equal to number of infusions within the last 12 months collected in the Hemophilia History form.

AIR combining retrospective and prospective data will be calculated as:

$$\frac{(\text{Number of infusions from baseline visit (Day 1) to end of study} + \text{Number of infusions collected in Hemophilia History form})}{(\text{Number of days from baseline visit (Day 1) to end of study} + 365.25)/365.25}$$

The annualized factor consumption will be calculated as:

The total factor replacement therapy consumption (in international unit [IU] and dose) x 365.25 days/number of days during the observation time period while the participant received factor prophylaxis replacement therapy in the usual care setting from baseline visit (Day 1) to end of study.

The number of bleeding episodes will be annualized using the same methods as the primary endpoint by spontaneous, traumatic and overall (treated and untreated) as defined in Protocol Appendix 2.

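### Appendix 2 and SAP 3.1 do not give one counting rule for untreated bleeds, so total ABR depends on which reading is programmed and can be overcounted

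*Protocol*

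**What the plan says.** Protocol Appendix 2 sets out when a bleed is new. For treated bleeds there is a single 72-hour condition: "A treated bleed occurring >72 hours after stopping treatment from the original bleed for which treatment was initiated", or a different site. For untreated bleeds there are two 72-hour conditions and a site condition. The definition opens with the two 72-hour conditions: "An untreated bleed occurring >72 hours after the previous untreated bleed at the same site or occurring >72 hours after stopping treatment". From the first *or* onward it reads: "or occurring >72 hours after stopping treatment from the original bleed for which treatment was initiated, or an untreated bleed occurring at a different site". All three are joined by *or*. Nothing ties the treatment condition to the most recent bleed.

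SAP 3.1 makes the primary endpoint ABR for treated and for total bleeds, and imports the definition: "Only new bleeds (as defined in Protocol Appendix 2) will be counted toward the number of bleeds for ABR calculation". It then adds a rule for untreated bleeds alone: "For untreated bleed, every occurrence will be counted as a separate bleed". SAP 3.2 annualises the number of bleeding episodes "by spontaneous, traumatic and overall (treated and untreated) as defined in Protocol Appendix 2". SAP 6.1.1 reports ABR for treated bleeds and for all bleeds.

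Protocol 1.2 says the prophylaxis efficacy data will be the control for efficacy after gene therapy in C0371002 and C3731003.

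**The concern.** A 72-hour rule exists so that one bleed, entered more than once, is counted once. For untreated bleeds the documents do not secure that, for two reasons.

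First, with *or* between the two conditions, meeting either is enough. Once treatment of some earlier bleed at a site ended more than 72 hours ago, every later untreated entry at that site meets the treatment condition, and the condition on the previous untreated bleed no longer merges anything. A bleed from weeks before, unrelated to the present one, then decides whether the filter works. Nothing in the documents explains why it should.

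Second, SAP 3.1 gives two instructions for the same count. One applies the Appendix 2 filter; the other applies none to untreated bleeds. Two programmers following the documents could produce different values of total ABR from the same diary.

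At stake are the all-bleed ABR and the overall and untreated bleed rates.

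**Working it through.** The plan states no expected ABR, share of untreated bleeds or rate of repeat entry, so there is no planned figure to reproduce. The check is of the logic, followed by an illustration and a sensitivity range on assumed inputs.

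**Candidate rules for an untreated entry at the same site**

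- *Literal or*: new if more than 72 hours after the previous untreated bleed, or more than 72 hours after treatment of an earlier bleed stopped.
- *Preceding bleed*: 72 hours measured from the most recent bleed, treated or untreated.
- *And*: both conditions must hold, where each earlier bleed exists.
- *Every occurrence*: the last SAP 3.1 sentence; no filter.

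**Illustration (assumed case).** One site. A treated bleed, with treatment stopped on Day 11. One untreated bleed entered on Days 100, 101 and 102. Follow-up is six months, 365.25/2 = 182.625 days, so each counted bleed adds 365.25/182.625 = 2.0 per year.

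- Literal or: Days 101 and 102 are only 24 hours after the previous untreated entry, but about 90 days after treatment stopped. All three entries are new.
- Preceding bleed, and *and*: Day 100 is new; Days 101 and 102 are not.
- Every occurrence: all three count.

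| Rule | Total ABR, earlier treated bleed at the site | Total ABR, no earlier treated bleed |
|---|---|---|
| Literal or | (1 + 3) × 2.0 = 8.0 | 1 × 2.0 = 2.0 |
| Preceding bleed | (1 + 1) × 2.0 = 4.0 | 1 × 2.0 = 2.0 |
| And | (1 + 1) × 2.0 = 4.0 | 1 × 2.0 = 2.0 |
| Every occurrence | (1 + 3) × 2.0 = 8.0 | 3 × 2.0 = 6.0 |

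With 12 months of follow-up all values halve. Treated ABR is 1 × 2.0 = 2.0 in the first column under every rule.

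The reverse order also matters. Take an untreated bleed on Day 30, a treated bleed at the same site on Day 60, and an untreated re-entry on Day 62. The re-entry is within 72 hours of treatment, but 32 days after the earlier untreated bleed. Literal *or* counts it; *and* does not.

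**Sensitivity range (all inputs assumed).** Per year, 4 treated and 4 untreated bleeds; 180 days of follow-up; treatment stops one day after the treated entry; each bleed is re-entered once as untreated within 72 hours with probability p; 20,000 simulated participants per scenario. For every occurrence the expected untreated rate is 4 + 8p, ignoring re-entries cut off at the end of follow-up. The total-ABR column adds 4 treated bleeds to each side.

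| Sites | p | Or | And | Every occurrence | Or v and, untreated rate | Or v and, total ABR |
|---|---|---|---|---|---|---|
| 3 | 10% | 4.15 | 3.91 | 4.8 | +6% | 8.15/7.91 = +3% |
| 3 | 25% | 4.51 | 3.91 | 6.0 | +15% | 8.51/7.91 = +8% |
| 3 | 50% | 5.14 | 3.88 | 8.0 | +32% | 9.14/7.88 = +16% |
| 1 | 10% | 4.32 | 3.71 | 4.8 | +16% | 8.32/7.71 = +8% |
| 1 | 25% | 4.99 | 3.71 | 6.0 | +35% | 8.99/7.71 = +17% |
| 1 | 50% | 6.12 | 3.63 | 8.0 | +69% | 10.12/7.63 = +33% |

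The *and* rule returns slightly less than the assumed 4.0 because it also merges some separate bleeds that fall close together at one site. Against 4.0, literal *or* gives from 4.15/4 = +4% to 6.12/4 = +53% on the untreated rate. These figures show how the rules separate; they do not estimate the effect in this study.

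**The case against.** A reader might infer that the word *or* by itself inflates total ABR and biases the control upward. The documents do not support that, for four reasons.

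1. The every-occurrence sentence in SAP 3.1 may govern. SAP 5.0 (19 September 2024) is later than Amendment 8 (31 March 2023), its history says the bleed-counting text was updated, and both documents let the SAP modify the protocol, short of a major change to the primary endpoint without an amendment. Under that sentence, changing *or* to *and* changes nothing: the illustration stays at 8.0, and at 6.0 with no earlier treated bleed. This stands. It does not settle the matter, because the SAP keeps the sentence limiting the count to Appendix 2 new bleeds and does not rank the two.
2. Appendix 2 refers to an original bleed as the index event. Its conditions can be read as alternatives according to whether that bleed was treated or untreated, and both anomalies above then disappear. This is a fair reading and may be the intended one. No words in the definition state it, so the wording remains ambiguous.
3. Site review may remove some repeats: diary compliance at least monthly (Protocol 5.2, 6.3), diary review at the end of study (6.5) and investigator review of diary bleeds for safety reporting (8.2.1). None is described as de-duplication. SAP 3.1 also accepts an infusion of any type within 72 hours when it classes a bleed as treated, subject to the bleeding diary or CRF, which may leave fewer untreated entries.
4. Upward bias of the control needs the counting rules of C0371002 and C3731003, which neither document gives. If the same rule is used there, both periods are affected.

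Appendix 2 makes the treated bleed the default protocol definition, and the SAP 3.1 formula counts treated episodes. That part of the primary endpoint is untouched.

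**Conclusion.** The plan lacks a single, unambiguous counting rule for untreated bleeds. Literal Appendix 2 wording, its reading by type of preceding bleed, and the SAP's every-occurrence sentence can give different counts from the same entries. Total (all-bleed) ABR and the overall and untreated rates depend on the choice and can be overcounted under the first and third.

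The illustration gives 8.0 against 4.0 per year for a participant with an earlier treated bleed, and 2.0 against 6.0 without one. Under the assumed re-entry probabilities, literal *or* exceeds *and* by 6% to 69% on the untreated rate, about half that on total ABR. The true size is unknown, since it needs the frequency of repeat untreated entries within 72 hours and the documents do not give it. Whether the comparison with gene therapy would be biased cannot be determined from these documents.

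The point is worth correcting before the final count is programmed, because it touches a named primary endpoint and the correction is small.

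**What to change.** Change both documents together; amending Appendix 2 alone has no effect if the SAP sentence is the one programmed.

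- **Protocol Appendix 2.** At the same site, call an untreated bleed new only when more than 72 hours have passed since the previous untreated bleed there **and** more than 72 hours since treatment ended for the previous treated bleed there, applying each condition where such a bleed exists. A bleed at a different site remains new.
- **SAP 3.1.** Delete the sentence "For untreated bleed, every occurrence will be counted as a separate bleed", or reword it so that it refers to this single rule. The overall and untreated rates in SAP 3.2 then follow it.
- Confirm which rule C0371002 and C3731003 use for untreated bleeds, so that the periods to be compared are counted alike.

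The cost is wording in two places and one program line, with no new data. Total ABR may come out somewhat lower; treated ABR does not change.
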